14.2 Study Populations

Subject disposition, demographics, and baseline assessments will be summarized using all enrolled subjects, whether or not the study drug was received.

[figure not shown]
The safety population will consist of all subjects who received any injection of study drug. All safety summaries will be based on this population.

[figure not shown]
The full analysis set (FAS) will consist of all subjects who received any injection of study drug and who have at least one post-baseline efficacy assessment. All efficacy summaries and analyses will be produced using this population and it will be considered the primary efficacy population.

14.4 Sample Size Determination

This study is open to subjects who participated in clinical study GLYX13-C-202 at specified investigative sites. Up to 100 subjects are eligible.

14.6 Pharmacokinetic Analysis

No pharmacokinetics samples will be obtained during this study.

15 ADMINISTRATIVE ASPECTS

15.1 Compliance with Regulatory Requirements

This protocol will be conducted in compliance with the protocol and all regulatory requirements, in accordance with Good Clinical Practices (GCP), including International Conference on Harmonization (ICH) Guidelines, and in general conformity with the most recent version of the Declaration of Helsinki.

15.2 Institutional Review Board Approval

This protocol, the informed consent document, and all relevant supporting data must be submitted to the IRB for approval. IRB approval of the protocol, informed consent document, and any advertisement used to recruit study subjects must be obtained before the study may be initiated.

The principal investigator is responsible for keeping the IRB advised of the progress of the study and of any changes made to the protocol as deemed appropriate, but in any case, at least once a year. The principal investigator is also responsible for notifying the IRB of any significant AEs that occur during the study.

The Sponsor will submit all protocol related documents for approval by the IRB for those sites able to use a central IRB.

15.3 Informed Consent

It is the policy of the Sponsor that written informed consent is obtained from subjects. The informed consent document must be signed and dated before the initiation of non-routine study-related tests, and before dosing of study drug. The original signed ICF for each participating subject shall be filed with records kept by the investigators(s). A copy of the informed consent document must be provided to the subject. If applicable, it will be provided in a certified translation of the local language. HIPAA requirements will be included in the ICF.

The subject's Bill of Rights will be included in the Informed Consent process in sites located in California.

15.4 Confidentiality

Personal study subject data collected and processed for the purposes of this study should be managed by the investigator and his/her staff with adequate precautions to ensure the confidentiality of those data, and in accordance with applicable national and/or local laws and regulations on personal data protection.

Monitors, auditors, and other authorized agents of the Sponsor, the IRB approving this research, and applicable regulatory authorities will be granted direct access to the study subjects' original medical records for verification of clinical study procedures and/or data, without violating the confidentiality of the subjects, to the extent permitted by the law and regulations. In any presentation of the results of this study at meetings or in publications, the subjects' identity will remain confidential.

15.5 Compensation, Insurance and Indemnity

Information regarding compensation, insurance, and indemnity is addressed in the Clinical Trial Research Agreement.

15.6 Protocol Amendment

If a protocol has been filed with regulatory agencies or submitted to an IRB and requires changes, a protocol amendment must be written. Any changes to the protocol will be made by the sponsor. All amendments will be sent to the IRB on the study sites' behalf. Sites using a local IRB are then responsible for submitting the amendment to their local IRB for approval.

15.7 Case Report Forms

An electronic CRF (eCRF) will be used to record all subject data specified by this protocol. The eCRF must be completed by designated and trained study personnel within 72 hours of the study visit. The eCRF will be signed by the principal investigator or a subinvestigator listed on the FDA Form 1572. It is the responsibility of the principal investigator to ensure the CRFs are completed and submitted to the Sponsor (or designee) in an accurate and timely manner. The processing of eCRFs will include an audit trail (to include changes made, reason for change, date of change and person making change).

15.8 Source Document Maintenance

Source documents are defined as the results of original observations and activities of a clinical investigation. Source documents may include, but are not limited to, study progress notes, e-mail correspondences, computer printouts, laboratory data, and drug accountability records. All source documents produced in this study will be maintained by the Investigator(s) and made available for inspection by Sponsor representatives, the FDA and any other applicable regulatory authorities.

15.9 Study Monitoring Requirements

Site visits will be conducted by an authorized Sponsor representative (the monitor) to inspect study data, subject's medical records, and CRFs in accordance with ICH guidelines, GCPs, and the respective US or national regulations and guidelines, as applicable. It will be the monitor's responsibility to inspect the CRFs at regular intervals throughout the study, to verify the adherence to the protocol and the completeness, consistency and accuracy of the data being entered. The monitor should have access to laboratory test reports and other subject records needed to verify the entries on the CRFs.

The Investigator will permit staff and contracted representatives of the Sponsor, the FDA, and/or respective health authorities to inspect facilities and records relevant to this study.

15.10 Study File Management

It will be the responsibility of the investigator(s) to assure that the study file at the site is maintained. The study file will contain, but will not be limited to, source documents, CRFs, and all other administrative documents, eg, IRB correspondence, clinical trial materials and supplies shipment manifests, monitoring logs, Sponsor correspondence, and so forth. A study-specific binder will be provided with instructions for the maintenance of study records.

15.11 Study Completion

The Sponsor requires the following data and materials before a study can be considered complete or terminated: source documents, completed, and signed CRFs.

15.12 **Audits**

During the course of the study, or after completion of the study, each study site may be subject to an audit by a Quality Assurance Auditor (or an auditor appointed by the Sponsor or its authorized representative) and/or an inspector from the FDA and/or other regulatory authority. Every attempt will be made to notify the Investigator in writing in advance of the audit.

15.13 Retention of Records

According to US Investigational New Drug (IND) regulations (21 CFR 312.62), records and documents pertaining to the conduct of this study and the distribution of study drugs including CRFs, ICFs, laboratory test results, and drug inventory records will be retained. These records will be kept on file by the principal investigator for 2 years after a marketing application is approved for the drug for the indication for which it is being studied. If no application is filed or approved, these records must be kept for 2 years after the investigation has been discontinued and the FDA has been notified. Per ICH guidelines, documents should be retained until at least 2 years after the last approval of a marketing application in an ICH region and until there are no pending or contemplated marketing applications in an ICH region, or at least 2 years have elapsed since the formal discontinuation of clinical development of the investigational product. The Sponsor will notify the investigator when records and documents no longer need to be retained. No study records should be destroyed without prior written authorization from the Sponsor.

15.14 Disclosure of Data

The investigator agrees by his/her participation that the results of this study may be used for submission to national and/or international registration and supervising authorities. If required, these authorities will be provided with the names of investigators, their addresses, qualifications and extent of involvement. It is understood that the Investigator is required to provide the Sponsor with all study data, complete reports, and access to all study records.

Data generated by this study must be available for inspection by the FDA and other regulatory authorities, by the Sponsor, and the IRB as appropriate. At a subject's request, medical information may be given to his or her personal physician or other appropriate medical personnel

responsible for his or her welfare. Subject medical information obtained during the course of this study is confidential and disclosure to third parties other than those noted above is prohibited.

15.15 Financial Disclosure

The FDA Financial Disclosure by Clinical Investigators (21 CFR 54) regulations require sponsors to obtain certain financial information from investigators participating in covered clinical studies; each principal investigator and subinvestigator is required to provide the required financial information and to promptly update the Sponsor with any relevant changes to their financial information throughout the course of the clinical study and for up to 1 year after its completion. This rule applies to all investigator(s) and subinvestigator(s) participating in covered clinical studies to be submitted to the FDA in support of an application for market approval.

15.16 Publication Policy

The publication policy is outlined in the Clinical Trial Agreement.

17 APPENDICES

LDH lactate dehydrogenase LDL low-density lipoprotein LLN lower limit of normal

MedDRA Medical Dictionary for Regulatory Activities

PCS potentially clinically significant

QTc QT interval corrected for heart rate

QTcB QT interval corrected for heart rate using the Bazett formula

 $(QTcB = QT/(RR)^{\frac{1}{2}})$

QTcF QT interval corrected for heart rate using the Fridericia formula

 $(QTcF = QT/(RR)^{\frac{1}{3}})$

SAE serious adverse event **SAP** Statistical Analysis Plan

SCI Structured Clinical Interview for Depression

GLYX13-C-203 Statistical Analysis Plan

Rapastinel (GLYX-13) Page 5

standard deviation SD

SI Le Système International d'Unités (International System of Units)

SOC system organ class

TBL total bilirubin

TEAE treatment-emergent adverse event

TESAE treatment-emergent serious adverse event

upper limit of normal ULN

2.0 INTRODUCTION

This statistical analysis plan (SAP) provides a more technical and detailed elaboration of the statistical analyses for efficacy and safety assessments as outlined and/or specified in the final study protocol and the most recent amendment (version 03 dated 23 Nov 2016).

This is a Phase 2, open-label, safety study of rapastinel (GLYX-13). Up to 100 subjects who participated in clinical study GLYX13-C-202 (NCT01684163), in which they completed 12 weeks of treatment of either rapastinel (GLYX-13) or placebo, will enter the extension study and receive additional rapastinel (GLYX-13) treatment. Participation in the study may continue until rapastinel (GLYX-13) is approved for marketing in the United States or until the study is ended by the Sponsor.

Following 1 month at the dose level, subjects who were assigned to placebo during the randomized withdrawal period of GLYX13-C-202 are eligible to participate, and will begin at the dose level to which the subject was assigned during the stabilization period of GLYX13-C-202. The investigator may continue the same dose level and dose interval, or may change the dose level and dose interval. The investigator will complete a treatment plan that outlines the dose level and dose interval at which rapastinel (GLYX-13) will be administered. The investigator, at the investigator's discretion, may change the treatment plan to alter dose level and/or dose interval based on the subject's depression status.

Investigator will begin treatment based on the dose level (5 mg/kg or 10 mg/kg) to which the subject was assigned during participation in GLYX13-C-202; subjects originally assigned to 5 mg/kg will receive 225 mg/3 mL, and subjects originally assigned to 10 mg/kg will receive 450 mg/3 mL. If subject experiences adverse event(s) (AEs) that the investigator believes may be associated with rapastinel (GLYX-13), the investigator may decrease dose level from 450 mg to 225 mg. If at any point the subject cannot tolerate the minimum 225 mg unit dose, the subject should be discontinued from the study. There are 3 dose groups (despite weekly or biweekly dosing schedule):

- Low dose group consisting of all subjects whose dose level is 225 mg or 5 mg/kg;
- High dose group consisting of all subjects whose dose level is 450 mg or 10 mg/kg;
- Mixed dose group consisting of all subjects who changed dose level between low dose (225 mg or 5 mg/kg) and high dose (450 mg or 10 mg/kg).

At the screening visit, the Structured Clinical Interview for Depression (SCID) will be administered to determine whether any exclusionary conditions have arisen since subject's completion of GLYX13-C-202. The Columbia Suicide Severity Rating Scale (C-SSRS) will be administered. A physical examination will be conducted to ascertain if significant changes have occurred since the subject ended participation in GLYX13-C-202. Blood and urine samples will be obtained for laboratory analysis. Antidepressant agents used since the subject ended participation in GLYX13-C-202 will be recorded.

[figure not shown]
On Week 1 Day 1, subjects will arrive at the investigative site having fasted for at least 10 hours, with water as desired. Each subject's eligibility will be confirmed; then a physical examination will be performed, and blood and urine samples for laboratory analysis will be obtained. Vital signs will be assessed and mass recorded. Electrocardiogram (ECG) will be recorded,

Each subject will then receive an intravenous (IV) dose of rapastinel (GLYX-13) (225 mg or 450 mg unit dose) in a "slow bolus" injection in an upper extremity vein within approximately 1 to 2 minutes. Subjects will be discharged following determination by the investigator that they are medically able to leave. The aforementioned procedures must be repeated within 24 hours before dosing if screening assessments were performed greater than 7 days before study drug dosing.

Subjects will return to the study site during the first month on the schedule (weekly or biweekly) to which they were assigned in GLYX13-C-202. After the first month, subjects will return to the study site on a schedule defined by the treatment plan set by the investigator.

Rapastinel (GLYX-13) will be administered. Subjects will remain in the study unit until determination by the investigator that they are medically able to leave the study unit.

. ECG will be recorded and blood and urine samples will be obtained for laboratory analysis. Rapastinel (GLYX-13) will be administered. Subjects will remain in the study unit until determination by the investigator that they are medically able to leave (see Schedule of Evaluations,

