6.3 Treatment Plan

Following one month at the dose level (subjects who were assigned to placebo during the randomized withdrawal phase of GLYX13-C-202 are eligible to participate and will begin at the dose level to which the subject was assigned during the stabilization phase of GLYX13-C-202) and dose interval to which the subject was assigned during the randomized withdrawal period of GLYX13-C-202, the investigator may continue the same dose level and dose interval, or may change the dose level and dose interval. The investigator will complete a treatment plan that outlines the dose level and dose interval at which rapastinel (GLYX-13) will be administered. The investigator, at the investigator's discretion, may change the treatment plan to alter dose level and/or dose interval based on the subject's depression status.

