14 STATISTICS

14.1 General Considerations

Quantitative assessments will be summarized using descriptive statistics including the mean, standard deviation, median, minimum and maximum values. Changes from baseline will be summarized where appropriate.

Qualitative assessments will be reported as frequencies and percents within each assessment level. Unless specified otherwise, the denominator for percents will the number of subjects in each treatment group. Shift tables may be produced for some assessments and will contain counts of subjects in each cross-classification level of baseline versus post-baseline assessment without percents. Only subjects with a baseline will be included in these tables but a missing category will be permitted for post-baseline values.

The baseline value for a given assessment will be the last non-missing observation collected before administration of study drug.

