3.0 OBJECTIVES

3.1 PRIMARY OBJECTIVE

The primary objective of this study is to examine the safety of long-term repeat exposure to rapastinel (GLYX-13) in subjects who participated in GLYX13-C-202.

The primary endpoint of this study is to examine the number of subjects who experience an AE over the course of the study.

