7.3 WEIGHT ADJUSTED DOSE OF RAPASTINEL

Per initial protocol, each subject received 5 mg/kg or 10 mg/kg in study GLYX13-C-203. In Amendment 3 of protocol, subjects originally assigned to 5 mg/kg in GLYX13-C-202 will receive 225 mg unit dose and subjects originally assigned to 10mg/kg in GLYX13-C-202 will receive 450 mg unit dose.

The dose of rapastinel for each subject will be divided by corresponding subject's weight assessed at the first visit at which each subject received either 225 mg unit dose or 450 mg unit dose and summarized descriptively by 225 mg or 450 mg treatment group for Safety Population. If subject had missing weight at that visit, the last non-missing weight assessment prior to that visit will be used in analysis.

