9.1 ADVERSE EVENTS

AEs will be coded using the *Medical Dictionary for Regulatory Activities* (MedDRA).

An AE (classified by preferred term) will be considered a treatment emergent adverse event (TEAE) if it was not present before the first dose of study drug or was present before the date of the first dose of study drug and increased in severity during the study period till the end of participation. If more than 1 AE was reported before the first dose of study drug and coded to the same preferred term, then the AE with the greatest severity will be used as the benchmark for comparison with the AEs occurring during the study. An AE that occurs more than 30 days after the date of the last dose of study drug will not be considered as a TEAE. An AE that becomes serious on or after the first dose of study drug will also be considered as TEAE.

The number and percentage of subjects reporting TEAEs will be tabulated by SOC and preferred term and further categorized by severity and causal relationship to study drug. If more than 1 AE is coded to the same preferred term for the same subject, the subject will be counted only once for that preferred term using the greatest severity and strictest causality for the summarization by severity and causal relationship. The distribution of TEAEs by severity and relationship to study drug will be summarized. An AE that occurs more than 30 days after the date of the last dose of study drug will not be summarized.

The incidence of common (in \geq 2% of subjects) TEAEs during the study period till the end of participation will be summarized by preferred term and will be sorted by decreasing frequency.

An SAE that occurred between the date of the first dose of study drug and 30 days after the date of the last dose of study drug, inclusive, will be considered a treatment-emergent SAE (TESAE). The number and percentage of subjects who have TESAEs will be summarized by preferred term. In addition, the incidence of on-therapy SAEs that led to death will be summarized separately by preferred term.

The incidence of TEAEs leading to premature discontinuation of study drug during the study period till the end of participation will be summarized by preferred term, and will be sorted by decreasing frequency.

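### The SAP's Low, High and Mixed dose groups depend on dose changes made after treatment starts, so an adverse event table split by them would not show the tolerability of 450 mg

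*SAP*

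**What the plan says.** SAP 2.0 (Introduction) names three dose groups, regardless of dosing frequency. The High group is "High dose group consisting of all subjects whose dose level is 450 mg or 10 mg/kg"; the Low group is the matching definition for 225 mg or 5 mg/kg. The third is "Mixed dose group consisting of all subjects who changed dose level between low dose (225 mg or 5 mg/kg) and high dose". No time limit, direction or reason for the change is given.

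Two routes lead to a change of level:

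- **Adverse event.** For an event thought to be associated with the drug, "the investigator may decrease dose level from 450 mg to 225 mg" (SAP 2.0; also Protocol 6.2).
- **Depression status.** After the first month the investigator "may change the treatment plan to alter dose level and/or dose interval based on the subject's depression status" (Protocol 6.3; repeated in SAP 2.0). No direction is specified.

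On reporting, SAP 9.1 says "The number and percentage of subjects reporting TEAEs will be tabulated by SOC and preferred term", with further breakdown by severity and causality; it names no dose grouping. Protocol 14.1 says that, absent another specification, "the denominator for percents will the number of subjects in each treatment group". The primary endpoint in SAP 3.1 is "the number of subjects who experience an AE over the course of the study", a whole-study count.

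**The concern.** A grouping variable for a safety table should not be something the safety outcome can change. Here it can. A subject who starts on 450 mg, has a suspected drug-related event and is reduced to 225 mg is classed as Mixed for the whole study, and the event that began on 450 mg is counted there. The visit windows in SAP 14.2 run to a scheduled Day 1820, so one change late in a period of about five years relabels everything before it.

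The stake is the dose-specific reading of the study's primary domain, long-term safety. If columns are headed Low, High and Mixed, a reader will naturally take the High column as the experience of 450 mg. It would be the experience only of subjects who never changed level. Mixed would combine events on both levels, in subjects who changed for different reasons and in either direction. This would arise even if every subject had received only fixed doses; pooling mg/kg with fixed doses is a separate question.

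**Working it through.** The plan gives no figure to reproduce: the sample size is a ceiling of 100, no inference is planned, and no split by dose, event rate or reduction rate is stated. The check is therefore algebra plus an illustration with assumed inputs.

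**Notation**

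- n = subjects starting at the high level (assumed 50)
- x = those who have the event while on it (assumed; 10 to 40)
- k = those among the x who are reduced because of it (assumed; 0 to 10)
- m = event-free subjects who change level for depression status (assumed; 0 to 10)

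**Formulas**

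- Rate by starting dose: x / n
- Rate in the SAP's High group: (x − k) / (n − k − m)
- Rate among these starters once classed as Mixed: k / (k + m)

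**Step 1: adverse event reductions alone (m = 0).** The inequality (x − k)/(n − k) < x/n is equivalent to n(x − k) < x(n − k), that is, xk < nk. This is true whenever k > 0 and x < n. So this route by itself always lowers the High rate. With x = 20 (40.0% by starting dose):

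| k | High rate |
|---|---|
| 2 | 18/48 = 37.5% |
| 5 | 15/45 = 33.3% |
| 10 | 10/40 = 25.0% |

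Over x from 10 to 40 and k from 2 to 10, the smallest fall is 0.8 points (x = 40, k = 2: 40/50 = 80.0% to 38/48 = 79.2%) and the largest is 20 points (x = 10, k = 10: 10/50 = 20.0% to 0/40 = 0.0%).

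**Step 2: add changes for depression status**, again with x = 20:

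| k | m | High rate | Mixed rate |
|---|---|---|---|
| 5 | 5 | 15/40 = 37.5% | 5/10 = 50.0% |
| 2 | 5 | 18/43 = 41.9% | 2/7 = 28.6% |
| 5 | 10 | 15/35 = 42.9% | 5/15 = 33.3% |

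The High rate now lies on either side of 40.0%. It falls below x/n only when the event rate among those who leave High exceeds the rate among all who started there. The two balance when k/(k + m) = x/n; for example k = 4, m = 6 gives 16/40 = 40.0%.

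**Step 3: the overall count.** In the last row, 15 events in High and 5 in Mixed add to 20 of 50. Events are moved, not lost, so the whole-study endpoint is unchanged.

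**Step 4: where the groups are used.** The visible SAP text names the three groups once, in 2.0. Disposition of the Safety Population, deviations, baseline data, exposure and compliance (SAP 5.0 to 7.2) are presented mainly overall. The one visible by-dose summary, weight-adjusted dose in SAP 7.3, is "summarized descriptively by 225 mg or 450 mg treatment group for Safety Population", which is a different split. SAP 9.1 specifies neither an overall column nor a grouping. No visible rule attributes an event to the dose at onset or the starting dose, and visible exposure is not split by dose level.

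**The case against.** The strongest reply is that the harmful table is not in the visible plan. SAP 9.1 mentions no dose groups, and the primary endpoint cannot be affected. Protocol 14.1 allows for exceptions and does not define Low, High or Mixed; Protocol 8.2 describes treatment groups by the dose level and frequency at which subjects begin, so starting dose is at least as natural a reading of its denominators. The text between SAP 7.3 and 9.0, and between the end of 9.1 and 10.0, is not in the public copy, so use of the groups there cannot be checked.

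That stands, and it makes the point conditional. It does not remove it. The three groups are the only complete set of dose groups the SAP defines, and they have no other visible purpose. Percentages default to treatment groups, and SAP 15.0 declares no departure from the protocol's analyses.

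A reader might go further and infer that the grouping makes 450 mg look safer. The documents do not support that. It requires both that events are tabulated by these groups and that reductions for adverse events dominate the changes; neither is stated, and changes for depression status can reverse the sign. Nor is anything hidden. Moved events would appear in a labelled Mixed column, subjects who stop on 450 mg for an event without an earlier change of level stay in High, and serious events and discontinuations for adverse events are summarised and listed separately.

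**Conclusion.** The point holds conditionally. Membership of Low, High or Mixed is settled by events after dosing starts, and a suspected drug-related adverse event is one of them. If adverse events are displayed by these groups, reductions for adverse events alone lower the High rate; with changes for depression status included, the net direction is unknown. Either way, neither High nor Mixed can be read as the tolerability of 450 mg.

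The sizes shown (a fall of 0.8 to 20 points from the first route alone; 37.5% to 42.9% against 40.0% in the mixed scenarios) are illustrations. They rest on an assumed 50 starters, assumed event and reduction counts, and the simplification that those changing for depression status are event-free. The documents contain nothing from which an actual size could be estimated. The overall primary count is not affected.

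**What to change.** State in the SAP where the three dose groups are used. For any safety summary by dose, replace them with one or both of these:

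- **Starting dose level in GLYX13-C-203**, which is fixed before any on-study event. It describes outcomes after starting at a level, not the dose in use at onset.
- **Dose level of the last injection before onset**, assigned to each treatment-emergent event, with subject-time or number of injections at that level as the denominator.

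Keep Mixed only as a descriptive count of subjects who changed level, with the reason where it was recorded. That qualification matters: the action-taken list in Protocol 12.7.4 has five categories and none for a reduced dose, and Protocol 6.3 describes the treatment plan as setting out level and interval, not the reason for a change.

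The cost is SAP wording and one derived variable from dosing records and event start dates that are already collected; time or injections at each level come from the same dosing records. The dose-at-onset table needs a footnote that subjects who switch appear under both levels. No dosing rule changes.
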